9.4 Statistical Analyses

Below is a description of planned statistical analyses. Further details are presented in the Statistical Analysis Plan (SAP).

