9.4.1 General Considerations

All statistical analyses will be conducted using SAS, Version 9.4 or later. Baseline characteristics will be summarized by treatment arm. For continuous measures the mean and standard deviation (SD) will be summarized. Categorical variables will be described by the proportion in each category. In addition, 95% confidence intervals (CIs) will be computed as indicated.

All the categorical variables including the primary endpoint will be summarized by treatment with the numbers and percentages of the participants. Treatment difference will be tested using a Cochran–Mantel–Haenszel test stratified by 1) country and 2) participant's clinical status at Baseline. For the categorical endpoints, relative risk and its 95% CI will be presented.

All of the continuous variables, including the changes from Baseline, will be summarized by treatment with the means, SD, medians and the ranges. The mixed model with repeated

measurements /analysis of covariance model with treatment, country, participant's clinical status at Baseline and visit as the model term, and Baseline value as the covariate will be used to test for the significance of the treatment difference. Least square means, standard errors, 95% CIs and p-values will be presented.

Time to event endpoints will be analyzed using the Cox Proportional Hazard model with treatment, participant's clinical status at Baseline and country as the model term. The hazard ratio of RESP301+SOC versus SOC will be presented along with 95% CI and p-value from the model. The Kaplan-Meier curves of the time to events will be presented by treatment for each applicable endpoint.

Handling of missing data

If participants are discharged from the hospital prior to Day 14 due to improvement of the clinical status and their status on Day 14 cannot be obtained, their status on Day 14 for the primary endpoint will be imputed with the status on the day of discharge. Depending on the reasons for missing data on the primary endpoint up to Day 14, additional sensitivity analyses will be performed. Further details on handling on missing data will be provided in the SAP.

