9.4.3 Secondary Endpoint(s)

The key secondary endpoints are:

1. Change from baseline on the modified WHO ordinal scale at each visit up to Day 28
2. Change in room air SpO₂ from baseline over time
3. Change in NEWS 2 symptom score from baseline over time
4. Time to improvement to a lower level (<4) of the modified WHO ordinal scale
5. Time to progression to a higher level (>4) of the modified WHO ordinal scale

Additional secondary endpoints are:

1. Time to hospital discharge
2. Incidence of mortality by Day 28

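### The repeated-measures model in Section 9.4.1 has no treatment-by-visit term, so it cannot estimate the WHO-scale endpoint at each visit or show how the SpO₂ and NEWS 2 effects change over time

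*Protocol*

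**What the plan says.** Section 9.4.1 gives one model for continuous variables and expressly includes changes from Baseline. It is a mixed model with repeated "measurements /analysis of covariance model with treatment, country", and the list continues with "clinical status at Baseline and visit as the model term, and Baseline value as the covariate will be used to test for the significance". What is tested is the difference between the arms. The outputs are described as follows: "Least square means, standard errors, 95% CIs and p-values will be presented". The section does not say whether these are per visit or overall. No interaction is listed.

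Section 9.4.3 names five key secondary endpoints. Three are changes from Baseline and would be served by this model:
- "Change from baseline on the modified WHO ordinal scale at each visit up to Day 28"
- "Change in room air SpO₂ from baseline over time"
- "Change in NEWS 2 symptom score from baseline over time"

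The other two are times to improvement and to progression, and fall under a separate rule: "Time to event endpoints will be analyzed using the Cox Proportional Hazard model with treatment".

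Section 9.4 opens with a general deferral: "Further details are presented in the Statistical Analysis Plan (SAP"). Nothing there or in 9.4.1 says that the term list is partial or that by-visit contrasts will be made.

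The text cited is that of Version 2.0 (Amendment 1). Version 1.0 lists the same terms. For Version 3.0 the summary of changes lists no change to 9.4.1 and the synopsis keeps the three endpoints, but its Section 9 is not in the material supplied.

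**The concern.** With treatment and visit as main effects only, the fitted mean profiles of the two arms are parallel. There is one treatment coefficient, and it stands for the difference on the first day after baseline, on Day 10 and, for the WHO scale, on Days 14 and 28 alike. An endpoint worded as change at each visit asks for differences that may vary by visit, so the stated model and the stated endpoint do not match.

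At stake are the estimates, intervals and p-values for up to three of the five key secondary endpoints. If the effect varies over the stay, the one number reported is a weighted average, with weights set by the covariance structure and by how many participants remain at each visit. If the gap is noticed only at analysis, the choice of contrast would be made in an open-label trial after interim data have been seen.

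**Working it through.** **The plan's own figure.** The protocol gives no power or precision for this model. Its only power statement is about 80% for the primary endpoint (200 v 100, 15% v 30%, one-sided 0.025). An unpooled z-test gives 0.15/√(0.30·0.70/100 + 0.15·0.85/200) = 0.15/0.0523 = 2.867 and Φ(2.867 − 1.960) = 81.8%, so the figure is consistent. It does not depend on the point made here.

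**Step 1: what the term list implies.** For visit j the listed model is: mean = visit effect(j) + τ × treatment + covariate terms. The between-arm difference is τ at every j. Adding treatment-by-visit replaces τ with τ(j). This follows from the terms alone.

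**Step 2: simulation check.** Assumed: 10 visits, SD 1, within-participant correlation 0.6, 200 v 100, no missing data.

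| True effect, first to last visit | Listed model: one effect | With interaction: visits 1, 5, 10 |
|---|---|---|
| 0.3 throughout | 0.30 | 0.29, 0.30, 0.30 |
| 0 to 0.6 | 0.30 | −0.01, 0.26, 0.60 |
| 0.6 to 0 | 0.31 | 0.61, 0.33, 0.01 |
| +0.4 to −0.4 | 0.00 | 0.39, 0.04, −0.39 |

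The listed model is right only when the effect is constant.

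**Step 3: size under stated assumptions.** Assumed: complete data, daily visits on Days 2 to 10 (t = 1 to 9), unit variance at each visit, 200 v 100. The generalised least squares weights are w = V⁻¹1/(1′V⁻¹1). The expected estimate as a fraction of the Day 10 effect is r = Σ w(t)δ(t), with δ scaled to 1 at Day 10. The variance of the common contrast relative to a Day 10 contrast is v = 1/(1′V⁻¹1). If the Day 10 contrast has 80% power (1.960 + 0.842 = 2.802), the power of the common contrast is Φ(2.802·r/√v − 1.960).

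- Compound symmetry, 0.6: equal weights; v = (1 + 8·0.6)/9 = 0.644.
- AR(1), 0.8: end visits weigh 1 and interior visits 0.2, over a total of 2 + 7·0.2 = 3.4; v = 1.8/3.4 = 0.529.

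Linear build-up, δ = t/9:
- Both structures: r = 5/9 = 0.556 (for AR(1), by symmetry).
- Compound symmetry: 2.802·0.556/0.803 = 1.94; power 49%.
- AR(1): 2.802·0.556/0.728 = 2.14; power 57%.

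Plateau by Day 5, δ = min(t/4, 1):
- Compound symmetry: r = 7.5/9 = 0.833; 2.802·0.833/0.803 = 2.91; power 83%.
- AR(1): r = (0.25 + 0.2·6.25 + 1)/3.4 = 0.735; 2.802·0.735/0.728 = 2.83; power 81%.

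**Step 4: discharge.** SpO₂ and NEWS 2 are scheduled only while the participant is hospitalized, up to Day 10 or discharge. Assume ignorable discharge falling linearly to 40% observed at Day 10. The Day 10 contrast that had 80% power then has 51–57%. The common contrast has 29–34% under linear build-up and 64–67% under the plateau. Which contrast does better therefore depends on the time course.

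**The case against.** **The SAP will settle it.** Interactions, covariance structure and reporting visits are often left to the SAP, and Section 9.4 defers detail there. This stands for the covariance structure and for the choice of test visit. It does not dispose of the main point: 9.4.1 does not leave the model open but lists its terms and says they will be used to test the treatment difference. The SAP may add the interaction. The protocol's list still does not match its own endpoint.

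**The slash allows ANCOVA.** A separate ANCOVA at each visit would serve an endpoint defined at each visit. But visit is itself listed as a term, and a by-visit ANCOVA would not contain it.

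**The WHO scale is ordinal.** Whether a seven-level scale falls under the continuous or the categorical rule of 9.4.1 is not wholly explicit. The continuous rule names changes from Baseline, so it is the natural reading.

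**Over time can mean on average.** This stands for SpO₂ and NEWS 2: Section 9.4.3 names no visit for them, and a treatment-period average is legitimate. It cannot be said of an endpoint defined at each visit.

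**The effect need not build.** A reader might infer that it must start near zero and grow, so that the listed model always dilutes it and a real effect would be missed. The documents give no time course. For the WHO scale the arms do start equal, because all participants enter at level 4. For SpO₂ and NEWS 2 the build-up is an assumption, and in the plateau case the averaged test loses no power.

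**Day 10 is the sparsest visit.** A reader might also conclude that Day 10 should be the test visit. Section 9.4.3 does not require that. After discharges a Day 10 contrast rests on the fewest participants, and on a selected group.

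**Conclusion.** The point holds, in limited form. Followed as written, Section 9.4.1 gives one treatment difference common to all visits. It cannot deliver the WHO-scale endpoint at each visit up to Day 28, and it cannot show how the SpO₂ and NEWS 2 effects change over time. That conclusion needs no numerical assumption.

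The size does. With complete data on Days 2 to 10 and linear build-up, the single contrast is 56% of the Day 10 effect, with 49% or 57% power against 80%. With a plateau by Day 5 it is 74–83% of the Day 10 effect, with power of 81–83%. The constant failure is in estimation by visit. Loss of power depends on the time course.

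This is worth correcting but not critical. It concerns three of the five key secondary endpoints, and the mismatch is unambiguous for one of them. The primary analysis (Cochran–Mantel–Haenszel), the sample size and alpha are unaffected. That the wording persists in Version 3.0 is likely from its change table but could not be confirmed.

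**What to change.** In Section 9.4.1:
- Add treatment-by-visit to the term list, and preferably Baseline-by-visit. The latter carries information only for SpO₂ and NEWS 2, since by inclusion criterion 3 all participants enter at level 4 on the WHO scale.
- State that the WHO-scale difference is reported at each visit up to Day 28.
- State for SpO₂ and NEWS 2 whether the test is at a named visit or is an average over visits taken from the same model. Either is defensible; the choice is the sponsor's and should be fixed before unblinded interim data exist.

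The covariance structure, with a fallback in case it does not converge over this many visits, can go in the SAP.

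**Cost.** One or two sentences and no new data. The richer model uses a few more degrees of freedom and still allows an averaged contrast. Visit-specific intervals are wider, most of all at late visits after discharges. Under the 40% assumption above, a fall in Day 10 power from 80% to 51–57% corresponds to a standard error 2.802/2.138 = 1.31 to 2.802/1.974 = 1.42 times that with complete data.

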Approximately 300 adult (male or female) participants will be randomly assigned to study intervention (200 to the Investigational arm and 100 to the Control arm).

Intervention Groups and Duration:

The total study duration for a participant from screening to last follow up will be up to 30 days (± 2 days). The study will be divided into the following periods:

[figure not shown]
- Screening period: starts up to 2 days (48 hours) prior to and extends up to the day of treatment initiation (Day 1); Days -2, -1 and 1
- Intervention period: up to 10 days; Day 1 to Day 10
- Efficacy follow-up: Day 14 and Day 28 (both ± 2 days)
- Safety follow-up: 28 days after treatment initiation; with the participant being contacted by phone call, if not still hospitalized, on Day 28 (± 2 days)

Participants will be consented and randomized 2:1 to the Investigational arm or the Control arm. Participants randomized to the Investigational arm will receive inhaled RESP301 (6 mL) administered using a nebulizer TID for up to 10 days in addition to the SOC, while participants in the Control arm will receive SOC alone.

Data Monitoring Committee: Yes

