1.3 Schedule of Activities (SoA)

Table 1-1 Schedule of Activities (SoA)

Procedure	Screening (up to 48 hours before Day 1 ¹)	Intervention Period			Early withdrawal	Efficacy follow-up (Day 14) ² (± 2 days)	EoS efficacy and safety follow-up (Day 28) ² (± 2 days)	Notes
		Day 1 ¹	Daily while hospitalized	Day 10 / hospital discharge				
Informed consent	X							Optional tokenization ICF to be provided for a subset of participants in the United States (see Section 8.4)
Confirmation of COVID-19 infection by nasopharyngeal RT-PCR ³	X							
Inclusion and exclusion criteria	X	X						Recheck clinical status before 1st dose of study intervention
Demographics	X							
Physical examination including height and weight	X			X	X		X ²	Full physical exam and height only at screening

Procedure	Screening (up to 48 hours before Day 1 ¹)	Intervention Period			Early withdrawal	Efficacy follow-up (Day 14) ² (± 2 days)	EoS efficacy and safety follow-up (Day 28) ² (± 2 days)	Notes
		Day 1 ¹	Daily while hospitalized	Day 10 / hospital discharge				
Pregnancy test (urine)	X							All women, including women of childbearing potential and pregnant women, may be enrolled in the study. Pregnancy status should be recorded (see Section 8.3.5). Note: Only females of child bearing potential and pregnant females need to undergo a screening pregnancy test.
Medical history (includes substance usage)	X							History of substance usage or abuse to be recorded but is not exclusionary
Medication history	X							In the prior 3 months
Laboratory assessments (including liver chemistries) ⁴	X	X	X ⁴	X	X		X ²	
12-lead ECG	X							After resting supine for approximately 5 minutes. QRS, QT, QTcF, PR, RR, rate
Vital signs ⁵	X	X	X ⁵	X	X		X	Within 15 minutes prior to study intervention administration
Randomization		X						

Procedure	Screening (up to 48 hours before Day 1 ¹)	Intervention Period			Early withdrawal	Efficacy follow-up (Day 14) ² (± 2 days)	EoS efficacy and safety follow-up (Day 28) ² (± 2 days)	Notes
		Day 1 ¹	Daily while hospitalized	Day 10 / hospital discharge				
Study intervention, TID ⁶		X	X	X				A staggered dosing approach will be used for the first 10 participants (up to the first IDMC safety review). Each RESP301 dose will be administered by intermittent inhalation to monitor the tolerability and response to RESP301 (see Sections 6.1 and 9.6). Where possible study intervention should be administered at approximately the same times each day At least 6 hours between 2 consecutive doses

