8.1 Efficacy Assessments

8.1.1 Modified WHO Ordinal Scale

A modified WHO ordinal scale will be used for consistency with the recent study of lopinavir-ritonavir in adults hospitalized with severe COVID-19 (Cao et al, 2020), to record the participant's status at the time of assessment. The modified WHO ordinal scale includes the following levels:

1. Not hospitalized, no limitations on activities;
2. Not hospitalized, limitation on activities;
3. Hospitalized, not requiring supplemental oxygen;
4. Hospitalized, requiring supplemental oxygen;
5. Hospitalized, on non-invasive ventilation or high-flow oxygen devices;
6. Hospitalized, on invasive mechanical ventilation or extra corporeal membrane oxygenation (ECMO);
7. Death.

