9.4.2 Primary Endpoint

The primary endpoint is the proportion of participants who progress to level >4 of the modified WHO ordinal scale due to COVID-19 by Day 14.

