10.5 Appendix 5: Statistical Design Considerations

10.5.1 Some General Design Considerations

1. Binary primary endpoint: progression to critical stage/death up to Day 14
 - to be analyzed by a Cochran-Mantel-Haenszel (CMH) stratified for the factors used in the stratified randomization
 - subjects who withdraw from study treatment will be followed up until their primary endpoint outcome is known (i.e., up to Day 14 or progression to critical stage/death, whatever is first)
 - it is, therefore, not clear what current protocol synopsis text could mean: *If subjects are discharged from the hospital prior to day 14 due to improvement of the clinical status and their status on day 14 cannot be obtained, their status on day 14 for the primary endpoint will be imputed with the status on the day of discharge. and what the implications on statistical study characteristics could be. Further discussion is needed.*
2. Timing of the two planned interim analyses with stopping options is stated as

There are 2 interim analyses planned, the first interim analysis after the first 60 participants have completed day 10 of the observation period ... and a second interim analysis after 150 participants have completed day 14 of the observation period.

With the current text for the timing of the first interim analysis, it is not clear how many subjects will have been randomized at least 14 days prior to the interim data cut-off date and can therefore provide data for the binary primary endpoint (“progression to critical stage/death up to Day 14”).

For such a binary endpoint, Parexel does not recommend including any participant randomized less than 14 days prior to the interim data cut-off date (note this would be different to a study with a time-to-event endpoint) as

- for such participants not yet progressed, the outcome up to Day 14 is unknown and should not be imputed as “not progressed up to Day 14”
- for such participants progressed prior to Day 14, the outcome is known but their inclusion would bias the estimation of progression probability up to Day 14 in a upwards direction.

In order to set up the adaptive group-sequential study design, the following assumptions have been used:

- first interim analysis: a total of ≈ 39 participants randomized at least 14 days prior to data cut-off date
- second interim analysis: a total of $\approx 50\%$ of the initially planned number of participants randomized at least 14 days prior to data cut-off date.

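### The primary endpoint is cumulative to Day 14, but the missing-data rule is worded as a Day 14 status and scoring after Day 10 is point-in-time, so some true progressors could be counted as non-events

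*Protocol*

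**What the plan says.** Protocol 9.4.2 defines the primary endpoint as the "proportion of participants who progress to level >4 of the modified WHO ordinal scale due to COVID-19 by Day 14". Appendix 5 (10.5.1, item 1) treats it the same way: participants who stop study treatment are followed "up to Day 14 or progression to critical stage/death, whatever is first".

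The missing-data paragraph of 9.4.1 covers participants "discharged from the hospital prior to Day 14 due to improvement of the clinical status and their status on Day 14 cannot be obtained". For them, "their status on Day 14 for the primary endpoint will be imputed with the status on the day of discharge". Appendix 5 cites this rule, comments that "it is, therefore, not clear what current protocol synopsis text could mean", and closes by asking for more discussion.

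On data collection, 8.1.1 says the scale records the "status at the time of assessment". In the Schedule of Activities (1.3), the column "Daily while hospitalized" stands under the intervention period, which runs from Day 1 to Day 10. After the Day 10 or discharge assessment, the scale is next scheduled at Day 14 and Day 28, by phone for those already at home. The synopsis gives the window: "Efficacy follow-up: Day 14 and Day 28 (both ± 2 days".

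The full text of 9.4.1 and Appendix 5 is visible in Version 1.0 and Amendment 1. The available copy of Amendment 2 breaks off in the Schedule of Activities, but its table of changes lists none to 9.4.1, 8.1.1 or Appendix 5.

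**The concern.** A cumulative endpoint is settled at the first event; nothing that happens later can undo it. A status endpoint depends on one day. The definition is of the first kind and the missing-data rule is written for the second. Anyone discharged because of improvement is below level 5 on the day of discharge, so the rule can only ever impute a non-event, including for someone who had already progressed.

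The collection schedule raises a related problem. After Day 10 the form asks where the participant stands at the contact, not the worst level since the last assessment. Events can be missed or placed on the wrong side of Day 14.

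At stake are the number of primary events, hence power and the conditional power used at the second interim analysis. If the loss differs by arm, the relative risk is affected too.

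**Working it through.** **1. Reproduce the planned size.** Inputs from Protocol 9.2, 9.5 and Appendix 5: 30% (SOC) against 15% (RESP301+SOC), allocation 100 and 200, one-sided alpha 0.025 (0.0249 at the final analysis), about 80% power.

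- Unpooled: n(SOC) = (1.960 + 0.842)² × (0.30×0.70 + 0.15×0.85/2) / 0.15² = 95.5, so 96 and a total of 288.
- Pooled without continuity correction: 88 in SOC, total 264. With correction: 97, total 291 (294 at alpha 0.0249).
- Power at 100/200, alpha 0.025: 84.9% uncorrected, 81.3% continuity-corrected, 81.4% by one-sided Fisher exact test.

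The planned 300 is consistent with these figures. The sample size is not in question.

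**2. What the wording does to individual histories.**

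| History | By 9.4.2 and Appendix 5 | By the literal 9.4.1 rule or the schedule |
|---|---|---|
| Level 5 on Day 4, discharged improved on Day 12, not reached | event | non-event (discharge status) |
| Same, but reached on Day 14 | event | rule not triggered |
| Level 4 on Day 10, level 5 on Days 11 to 12, level 4 at the Day 14 contact | event | no scheduled assessment sees it |
| Contact on Day 12, level 5 on Day 13, resolved later | event | not covered by the contact |
| First level 5 on Day 15, contact on Day 16 | non-event | can be taken as an event |
| Death, or level 5 to 6 still present at the Day 14 contact | event | captured |

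**3. Size.** Let m be the share of true progressors scored as non-progressors. The documents give no value, so a range is shown. The observed rates become 0.30(1−m) and 0.15(1−m). Power at alpha 0.0249 (z = 1.962) is Φ{[d − 1.962·SE0]/SE1}, with SE0 pooled and SE1 unpooled.

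Worked at m = 10%: 27% against 13.5%, d = 0.135, pooled rate 0.18. SE0 = √(0.18×0.82×0.015) = 0.0471; SE1 = √(0.27×0.73/100 + 0.135×0.865/200) = 0.0505. Then (0.135 − 0.0923)/0.0505 = 0.845 and power is 80.1%.

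| m (equal in both arms) | Events lost per arm | Power, uncorrected | Power, continuity-corrected |
|---|---|---|---|
| 0 | 0 | 84.9% | 81.2% |
| 5% | 1.5 | 82.6% | 78.6% |
| 10% | 3 | 80.1% | 75.7% |
| 20% | 6 | 74.5% | 69.3% |

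Equal m leaves the relative risk at 0.50. At m = 20% the expected interim counts fall from 15/50 and 15/100 to 12/50 and 12/100. In the Appendix 5 table (10.5.3) this moves conditional power from 90% with no increase to 77% with a total of 321.

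**4. Unequal loss (illustration).** With 30% and 15% true, losing 10% of SOC and 20% of RESP301 progressors gives 0.12/0.27 = 0.44. The reverse gives 0.135/0.24 = 0.56, with power 61.8%. With no true effect (30% in both arms), the first pattern gives 27% against 24% observed and a one-sided rejection rate of about 8.4% instead of 2.49%.

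**The case against.** The best defence is that the rule need not bite. Imputation is for missing outcomes, and under 9.4.2 and Appendix 5 a progression recorded on Day 4 is already an outcome. The rule also needs two conditions together: discharge for improvement and an unobtainable Day 14 status. Progression to Day 10 is in the daily records, and the time-to-progression endpoint (9.4.3) needs its date. 9.4.1 also promises sensitivity analyses and further detail in the SAP, which is not available here. All of this stands, and it limits the size. It does not remove the conflict: the protocol itself fixes the rule for the primary endpoint in status terms, and its own appendix could not say what the rule means.

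The Day 11 to 13 gap is narrow, since the episode must both start and resolve between assessments. It narrows further if sites go on scoring inpatients daily after Day 10, but the schedule places that column in the intervention period. Adverse event and medication review at Day 14 may reveal an episode, but neither is named as a source for the endpoint. An SAP cannot restore what was never recorded.

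A reader might go further and infer that the whole endpoint is a Day 14 status. If one third of progressors had recovered by then, the rates would be 20% and 10%, and power about 66% (pooled) or 60% (unpooled). The documents do not support this. No section defines the endpoint so for all participants; 9.4.2 and Appendix 5 say otherwise; and the one-third share appears nowhere.

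**Conclusion.** The point holds as an inconsistency in the definition of the primary event plus a limited gap in collection. It does not show that recovered progressors will in general be scored as non-events: that follows only from the literal rule, and only for those discharged as improved and not reached.

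The loss is probably modest. As an illustration, suppose one third of progressors recover, all of these are discharged before Day 14, and 5% to 15% of them cannot be reached. Then the rule alone gives m = 0.333 × 0.05 = 1.7% to 0.333 × 0.15 = 5%, and uncorrected power stays near 83% to 84%. Missed Day 11 to 13 episodes would add to m by an amount the documents do not allow one to estimate. Both the shares and their equality across arms are assumptions. Equality deserves some caution in an open-label trial, although nothing in the documents shows that the loss would differ by arm or in which direction.

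The point should be settled before data are collected, because the collection gap cannot be repaired at analysis.

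**What to change.** - In 9.4.1, state that any level above 4 due to COVID-19 dated from randomization to Day 14 is a primary event whatever the later level, and that the discharge-status rule applies only to participants with no recorded progression.
- Delete the open query in Appendix 5 (10.5.1, item 1).
- At the planned Day 14 contact, and at Day 28 for those contacted early or missed, record the worst level since the last assessment and its date, including any readmission. Count only events dated by Day 14.

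Once events are dated, the ± 2-day contact window need not change. The cost is two sentences, one case report form item in contacts already planned, and some recall error for participants at home. The planning rates and the sample size of 300 stay as they are.
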